8.3 Selection of Study Population

8.3.1 Inclusion Criteria

Subjects must fulfill all the following inclusion criteria to be eligible for participation in the study, unless otherwise specified:

- Female.
- Capable of giving informed consent.
- Self-reported stress-type UI symptoms of \geq three months duration
- Diagnosis of stress predominant urinary incontinence based on MESA stress symptom score greater than MESA urge symptom score (percent of total possible urge score).
- UDI-6 score \geq 25
- Willing to participate in the 8-week study with follow up at 6-and 12-months, refraining from the pursuit of treatment for Stress Urinary Incontinence using other modalities (i.e. will not wear a pessary, participate in pelvic floor PT or surgery) during the first 8- weeks.

8.3.2 Exclusion Criteria

Subjects must not be enrolled in the study if they meet any of the following criteria:

- Absence of a vagina.
- Age $<$ 18 years.
- Stage 3-4 pelvic organ prolapse (as determined by POP-Q).
- Diagnosis of any neuromuscular disease.
- Non-ambulatory.
- Currently pregnant or $<$ 12 months post-partum.
- \leq 3 months after failed surgery for stress urinary incontinence.
- Previous pelvic floor muscle training (PFMT) within the last 12 months under a supervised therapeutic plan of care.
- Currently taking, or has taken within the last 2 months, medication to treat urinary incontinence.
- Prior augmentation cystoplasty or artificial sphincter.
- Implanted nerve stimulator for urinary symptoms.

- Participation in another clinical study within 30 days of screening.
- Impaired cognitive function.
- Contraindication to the use of a vaginal probe.
- Unable to understand instructions on the use of the leva® Plus Pelvic Digital Health System.
- Unable to actively recruit the pelvic floor muscles to any degree for attempted volitional contraction.

8.3.3 Removal of Subjects from the Study

Subjects are free to withdraw from the study at any time for any reason.

In addition, subjects may be withdrawn from the study by the PI in consultation with the Sponsor for the following reasons:

- Subject is unable to use the *leva* device;
- Subject experiences a SAE;
- Protocol violation.

The clinical report will include reasons for subject withdrawals.

8.3.4 Prohibitions and Concomitant Therapy

There are no prohibited therapies, activities or medications except as described in the exclusion criteria. All medications taken by subjects during the study will be recorded.

8.4 Treatments

8.4.1 Treatment Administered

Subjects will train twice daily for 8- weeks using the *leva* device (for the treatment group) or Kegel exercises (for the control group).

8.4.2 Treatment Compliance

The *leva* device sends deidentified subject training and testing data to a secure, HIPAA compliant database, and subjects will receive periodic text messaging with training trips, reminders and motivational messages. Those in the Kegel control group will not be monitored for treatment compliance.

9 STUDY PROCEDURES

The Study Events Flow Chart ([Section 4](#)) summarizes the procedures to be performed at each visit. Individual procedures are described in detail below. Additional evaluations/testing may be deemed necessary by the PI and/or the Sponsor for reasons related to subject safety.

Any nonscheduled procedures required for urgent evaluation of safety concerns take precedence over all routine scheduled procedures.

9.1.1 Adverse Events

9.1.1.1 Monitoring

Subjects will be monitored at each study visit for adverse events. A specific enquiry will be made at the time of each check-in. The subjects will be queried with an open-ended question such as “How are you feeling?” or “How have you been feeling since your last visit?”

9.1.1.2 Serious Adverse Event

Any SAE will be reported to the Sponsor and the Institutional Review Board (IRB), as required. All SAEs will be reported to the Sponsor via fax or e-mail within one working day of becoming aware of the event, whether or not the serious events are deemed study treatment-related and within 5 working days to the IRB (24 hours of discovery if the event involves a death), as required.

An SAE is any AE or suspected adverse reaction that in the view of either the PI or Sponsor, results in any of the following outcomes: Death, a life-threatening adverse event, inpatient hospitalization or prolongation of existing hospitalization, a persistent or significant incapacity or substantial disruption of the ability to conduct normal life functions, or a congenital anomaly/birth defect. Important medical events that may not result in death, be life-threatening, or require hospitalization may be considered serious when, based upon appropriate medical judgment, they may jeopardize the subject and may require medical or surgical intervention to prevent one of the outcomes listed in the above definition.

Life-threatening is defined as an AE or suspected adverse reaction that in the view of the PI or Sponsor, its occurrence places the patient or subject at immediate risk of death. It does not include an adverse event or suspected adverse reaction that, had it occurred in a more severe form, might have caused death.

Treatment of SAEs will be performed by a physician, either at the site or at a nearby hospital emergency room. Where appropriate, medical test(s) and/or examination(s) will be performed to document resolution of event(s). Outcome may be classified as resolved, improved, unchanged, worse, fatal, or unknown (lost to follow-up).

If a SAE occurs to a subject on this study, contact the Sponsor’s Representative listed in [Section 2](#).

10 DATA ANALYSIS

Data will be handled and processed according to Operating Procedures, which are based on the principles of GCP.

10.1 Statistical Methods

Detailed methodology for summary and statistical analyses of the data collected in this study will be documented in the Clinical Study Report.

10.1.1 Determination of Sample Size

This planned randomized controlled trial is a tertiary prevention trial, comparing the efficacy of the Leva device in the treatment of stress urinary incontinence to standard pelvic floor muscle training, consisting of office education and a home exercise program. Our primary outcome is the proportion of subjects who are very much better/much better as measured by the PGI-I. Sample size for 20% difference between groups given a 30% success rate of home exercise programs, $\alpha=0.05$, and a power of 0.8, the needed sample size is 93 patients in each arm. Allowing for an attrition rate of approximately 15%, we require approximately 225 patients.

10.1.2 Subjects to Analyze

Safety Population: All subjects who were administered at least one training session will be included in the safety evaluations.

Efficacy Population: All subjects who had at least one *leva* testing administration and measurement of any of the efficacy assessments post Screening Visit.

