 - 4) Health Care Provider will perform a Pelvic Organ Prolapse Quantitative (POP-Q) assessment (If not completed at screening)
 - 5) The PFDx device will be then used to measure the pelvic floor angles and strength. This will be supervised by clinical research personnel blinded to randomization.
 - 6) To optimize blinding to arm, the randomization will occur following the above surveys and evaluations.

Following randomization, the subject will participate in one of two main study arms:

KEGEL STUDY ARM

- Subjects randomized to the Kegel Arm will receive standardized written and verbal instructions on how to perform three times daily/7 days per week pelvic floor muscle exercises and their ability to perform the correct muscle action will be confirmed by physical exam (written instructions per the handout, adapted from Voices for PFD). They will be instructed to perform these exercises three times daily throughout the 8-week study period, based on a commonly used kegel regimen. These instructions will occur during the baseline visit. Also at the baseline visit, subjects will be informed they will be asked to attest to the fact that they performed these exercises twice daily at least 80% of the time (approximately 17 times per week). This attestation will ask the subject to recall their adherence; no diary or other record will be required.
- Subjects will return to the office on week 4 to participate in validated questionnaires and undergo a progress evaluation using the PFDx. For clinical questions they will be directed to follow up with their physician. Their evaluator will be blinded to their randomization.
- Subjects will return to the office on week 8- to participate in validated questionnaires, undergo progress evaluation using the PFDx, and physical examination including a POP-Q and Brinks score, and attest to their adherence. Their evaluator will be blinded to their randomization
- Following week 8, patients will be recommended to continue weekly Kegel exercises, but will be free to pursue alternative treatments if desired. They will participate over the phone and via email or mail in validated questionnaires, in addition to reporting what (if any) additional therapies they have undergone for treatment of stress urinary incontinence at 6 months and 12 months after baseline.

LEVA STUDY ARM

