- At 6- and 12- months they will participate in validated questionnaires (see chart) by phone and email or mail, in addition to reporting what (if any) additional therapies they have undergone for treatment of stress urinary incontinence at 6 months and 12 months after baseline.
- The third party research center will provide a single phone call to the subjects receiving the leva plus to ensure the device is functioning properly. If there are questions regarding the device function, a conference call will be undertaken to allow the subject to trouble-shoot device function with the sponsor technical specialist. The sponsor will at no time possess protected health information (PHI)

VISIT CONTENT

At week 4 all study participants will return to the office to undergo a PFDx evaluation of pelvic floor muscle function and complete and return the following questionnaires:

- a. PFDI
- b. PISQ-IR
- c. McGill Pain Questionnaire
- d. SESPPFE
- e. Patient Global Impression of Severity and improvement (PGI-S, PGI-I) Scale
- f. WHODAS
- g. PFIQ

At week 8 all study participants in both arms will return to the clinic for the PFDx device evaluation of pelvic floor muscle function and physical examination including a POP-Q and Brinks score, and the following questionnaires:

- a) PFDI
- b) PISQ-IR
- c) McGill Pain Questionnaire
- d) SESPPFE

- e) PGI-S and PGI-I
- f) WHODAS
- g) PFIQ
- h) Attestation of 80% or greater compliance with exercises twice daily as per protocol

The 6 and 12 months follow-up by phone and email or mail will include:

- i) PFDI
- j) PISQ-IR
- k) McGill Pain Questionnaire
- l) SESPPFE
- m) PGI-S and PGI-I
- n) WHODAS
- o) PFIQ

PFDx device pelvic floor muscle evaluation for both study arms will include:

- Baseline pelvic floor muscle vaginal angle (at rest)
- Pelvic floor muscle vaginal angle with Valsalva
- Pelvic floor muscle angle with relaxation
- Pelvic floor muscle angle with muscle contraction
- Number of repetitions of contraction in 15 seconds;
- Maximum time a subject can sustain a pelvic floor muscle contraction.

This evaluation will be conducted using the PFDx device placed in the vagina by the subject and conducted by study staff using an automated measurement protocol.

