The *leva Plus* Incontinence System™ is a next-generation device currently under development. It has the same Indications for Use and Intended Use as the *leva* Incontinence System™. The primary differences between *leva* and *leva Plus* are as follows: (1) the *leva Plus* device combines the vaginal insert and control box into a single, smaller form that eliminates the need for a cable; (2) the *leva Plus* device has a small, detachable battery pack at the base; (3) the *leva Plus* device is made of a biocompatible thermoplastic elastomer, whereas *leva* is made of biocompatible silicone; and (4) the *leva Plus* device uses a Bluetooth Low Energy radio whereas the *leva* devices uses a classic Bluetooth radio. The *leva Plus* device communicates with an iPhone or Android mobile phone and provides biofeedback to the patient in the same way that *leva* does.

leva Plus Inco

**Image shows
from the batte**

hed

The *leva Plus* device has not been submitted to FDA for approval yet. However, it is being developed under appropriate Design Controls and Risk Analysis, as defined by FDA's 21 CFR 820 and ISO 13485. Renovia plans to submit a 510k application to FDA by late summer 2017. Given the similarity of *leva Plus* and *leva*, along with independent risk analysis, *leva Plus* is considered a “non-significant risk device” as defined by 21 CFR 812.3(m).

PFDx

The *PFDx* device is an investigational medical device currently used to gather data related to pelvic floor health. It uses

PFDX device

substantially equivalent technology to the *leva* Incontinence System, an FDA-approved, Class II medical device. Whereas the *leva* device uses 6 accelerometer sensors, the *PFDx* device uses 12 sensors, allowing for a more complete evaluation of a woman's physiology. The *PFDx* device is shaped as a ring that sits in the fornix with a thin, flat strip that descends along and out of the vagina. At the end of the device (outside the woman's body) is a small enclosure that houses a microprocessor and a Bluetooth Low Energy radio. The *PFDx* communicates wirelessly to a laptop or mobile phone, in a similar manner to the *leva* device. All sensors related components are over-molded with the same biocompatible silicone material used to manufacture the *leva* device. Given the similarity of *leva Plus* and *leva*, along with independent risk analysis, *leva Plus* is considered a "non-significant risk device" as defined by 21 CFR 812.3(m).

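### The Safety Population is keyed to a training session, so a woman who has an adverse event at the PFDx insertion before randomisation and stops there falls outside the safety set

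*Protocol*

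**What the plan says.** Protocol section 10.1.2 sets the rule: "Safety Population: All subjects who were administered at least one training session will be included in the safety evaluations". It does not mention exposure to PFDx.

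The order of the baseline visit is in section 8.1 under Visit #1. Item 5 reads: "The PFDx device will be then used to measure the pelvic floor angles and strength". Item 6 reads: "To optimize blinding to arm, the randomization will occur following the above surveys and evaluations". Arm-specific instruction (Kegel) or training (leva) comes next, at the same visit.

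Section 8.2 says that PFDx "is an investigational medical device currently used to gather data related to pelvic floor health". Section 8.1 gives the route: "This evaluation will be conducted using the PFDx device placed in the vagina by the subject". The evaluation applies to both arms, and the flow chart in section 4 schedules it at baseline, week 4 and week 8.

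On adverse events, section 9.1.1.1 asks for an enquiry at every study visit, made at check-in. Section 10.2 has adverse events followed for the whole study and safety data listed for each subject. The flow chart marks complications at weeks 4 and 8 only.

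The SAP does not mention the Safety Population and plans no safety analysis. Its section 3.5 uses the women randomised to each group as the denominator for all data.

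**The concern.** A safety set should contain everyone exposed to an investigational device. Here the first such exposure comes before the act that admits a woman to the set. If she has pain, bleeding or distress at the first PFDx insertion and leaves, the rule omits her, and the reason for the omission may be the harm itself. Exclusion that depends on the outcome biases a safety summary towards reassurance, and in a small trial one or two omitted women matter.

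The admitting act is also unclear for controls. Leva women complete a full device session at baseline. For Kegel women a training session could mean the clinic instruction or the home exercise. The two readings can give different control denominators.

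**Working it through.** No figure in the plan measures this gap, so the check is mainly a reading of the rules against the visit sequence.

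**Step 1: who is counted.** Every woman below has had the baseline PFDx insertion.

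| Point at which she stops | Protocol Safety Population (10.1.2) | SAP denominator (3.5) |
|---|---|---|
| After insertion, before randomisation | Out | Out |
| After randomisation, before instruction or training | Out | In |
| Leva arm, after the baseline device session | In | In |
| Kegel arm, after clinic instruction, no home exercise | Depends on the meaning of training session | In |

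The first row is covered by neither document. The second is covered only by the SAP, which plans no safety analysis.

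**Step 2: is the event recorded?** By section 9.1.1.1 it should be, since baseline is a study visit. Two details weaken this. The flow chart has no complications entry at baseline. The enquiry is tied to check-in, which, if that means arrival, precedes the insertion at the same visit. The next scheduled enquiry is at week 4, which a woman who has left does not attend.

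**Step 3: the control arm.** Section 8.1 has Kegel women instructed at baseline, with correct muscle action confirmed by examination. A site can document that. Section 8.4.1 uses training for the eight weeks of exercise, and section 8.4.2 says: "Those in the Kegel control group will not be monitored for treatment compliance". Section 8.1 requires no diary. The protocol does not say which sense section 10.1.2 intends.

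**Step 4: possible size.** The documents do not give the share of women who stop between insertion and training. Assume f from 0% to 5%. The inputs are 60 women enrolled (SAP section 2) and 225 planned (protocol section 10.1.1). Women omitted = N × f:

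| Assumed f | N = 60 | N = 225 |
|---|---|---|
| 0% | 0 | 0 |
| 1% | 0.6 | 2.25 |
| 2% | 1.2 | 4.5 |
| 5% | 3.0 | 11.25 |

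The choice of base matters little. If 60 is the number left after a 5% loss, the number lost is 60/0.95 − 60 = 3.2.

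The sample size calculation is unaffected.

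**The case against.** The strongest reply is that the events are not lost. Sections 9.1.1.1 and 10.2 require adverse events to be asked about and listed, and neither is limited to the Safety Population. Section 9.1.1.2 requires every serious event to be reported whether or not it is attributed to study treatment. The window is part of one visit, and the SAP denominator takes in women who were randomised but never trained. All of this stands, and it narrows the point: what is lost is membership of the safety set and its denominator, not necessarily the record. It does not remove the point. A listing supplies no denominator, and a woman who was never randomised is in neither count.

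A reader might infer more than the documents support:

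- **That control membership cannot be verified.** This follows only if a training session means home exercise. Section 10.1.2 speaks of sessions being administered, which fits the documentable clinic instruction at least as well. The statement in section 8.4.2 concerns adherence, not whether instruction was given. The fair criticism is that the term is undefined.
- **That PFDx events cannot be told from leva Plus events.** The case report forms are not among the documents, so a field for device or relatedness may exist. At group level, Kegel women receive PFDx without leva Plus and so show the background with PFDx alone.
- **That the gap is as large as the total number of insertions.** Three per woman would be 60 × 3 = 180, or 225 × 3 = 675. Insertions at weeks 4 and 8 ordinarily occur in women already trained, so only the first one bears on this gap.
- **That the risk statement under the PFDx heading in section 8.2, which names leva Plus, is further evidence.** It has no bearing on who is in the safety set.

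**Conclusion.** The concern holds in a limited form. The stated rule can omit a woman because of an event at her first exposure to an investigational device, and the SAP does not repair this for a woman who is never randomised. The conclusion rests on the written order of the baseline visit and on reading section 10.1.2 as a complete definition of the set, which is how an analysis population is normally read.

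The size is unknown. Under the assumed 0% to 5% loss it is 0 to 3 of 60, or 0 to about 11 of 225, and it may well be nil. The documents do not show that any such woman exists or that any event went unrecorded. The change is still worth making: it is cheap, and it removes a rule that excludes on harm.

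**What to change.** - Define the safety set as all women with at least one insertion of PFDx or leva Plus, or any training, whether or not randomised.
- Summarise events before randomisation separately, and later events by randomised arm.
- State that the baseline Kegel instruction counts as the control training session.
- Add complications at baseline to the flow chart, to agree with section 9.1.1.1, and make clear that the period after the PFDx measurement is covered.
- If the case report form does not already do so, record the device or activity associated with each adverse event (PFDx, leva Plus, exercise only, none).
- State in the SAP that safety summaries use this set and not the randomised denominator of section 3.5.

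The cost is a few sentences and at most one data field. The small downside is that the safety set may include a few women without an arm. Because the SAP reports that enrolment ended early at 60 women, the set and the classification of events can still be fixed in the SAP and report from existing records, while the flow chart and form changes help only a future trial under this protocol.

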10.2 Safety Evaluation

Safety data will be populated in individual CRFs. All safety data will be listed by subject.

AEs and SAEs will be monitored throughout the study. All SAEs will be recorded and reported. Concomitant medications and medical history will be listed by subject.

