4 STUDY EVENTS FLOW CHART

Intervention and outcomes	Screening Visit	Baseline	4 weeks	8 weeks	6 months	12 months
Eligibility and informed consent	x					
Urine Pregnancy Test (if indicated)	x					
UDI-6	x					
Medical History	x	*				
MESA questionnaire	x					
POP-Q	x [#]			x		
Brinks Scale		x [*]		x		
Primary Outcome Measures (PFDI, PGI-I, PGI-S)		x	x	x	x	X
PFDI, WHODAS, PISQ-IR, McGill Pain Questionnaire, SESPPFE, PGI-S, PGI-I, PFIQ		x	x	x	x	X
PFM performance assessment (PFDx)		x	x	x		
3-day voiding diary	x (before baseline visit)			x		
CGI-S, CGI-I	x			x		
Complications			x	x		
Follow up questions detailing further treatments for SUI					x	X

*May be done at screening visit if < 3 months prior to baseline visit

May be from a visit within 3 months of baseline visit.

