- Subjects randomized to the leva® Plus Pelvic Digital Health System will receive training on the use of the Leva® Plus Digital Health System including installation of the Digital Health System app, the completion of a training module, a timed lift test and one full leva exercise session of five timed lifts. Training will occur at the baseline visit. Subjects will be instructed to perform the lifts twice a day, for 2 ½ minutes each session, 7 days a week for a total of 8- weeks. Subjects will be informed they will be asked to attest to the fact that they performed these exercises twice daily at least 80% of the time (approximately 11 times per week). This attestation will ask the subject to recall their

adherence; no diary or other record will be required, although they will also be informed that the leva digital system tracks adherence. During the study period (8-weeks) subjects with the leva will contact the Renovia Patient Care Engagement team with any technical questions or issues regarding leva use. They will receive regular (6 days/week) text messages based on their performance of pelvic floor muscle exercises using the Leva device using predetermined algorithm for content. For any clinical questions they will be directed to their physician's office to speak with a healthcare provider.

- Subjects will return to the office on week 4 to participate in validated questionnaires (see chart) and undergo progress evaluation using the PFDx device. For clinical questions they will be directed to follow up with their physician. Their evaluator will be blinded to their randomization.
- Subjects will return to the office on week 8 to participate in validated questionnaires (see chart) and undergo progress evaluation using the PFDX device and physical examination including a POP-Q and Brinks score, and attest to their adherence. Their evaluator will be blinded to their randomization.
- Following week 8, patients will be recommended to continue weekly pelvic floor muscle exercises using the leva device but will be free to pursue alternative treatments if desired. Based on initial sub-randomization, subjects will receive periodic standardized text messages reminding them to use the leva over the next 10 months or receive no additional contact via the leva device.

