8.1.1 Confinement and Return Visits

The screening and baseline visit may be combined into one visit and take up to 1.5 hours. The visit at 4 weeks may take up to 1 hour. The end-of-study visit may take up to 1.5 hours. There are no other scheduled visits for this study. Follow up phone calls may take up to 45 minutes. See Study Events Flow Chart ([Section 4](#)).

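### Scheduled adverse-event enquiry ends at week 8 although leva use is recommended beyond it, and neither protocol nor SAP plans a by-arm safety summary

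*Protocol*

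**What the plan says.** **Collection.** Protocol 10.2 states that "AEs and SAEs will be monitored throughout the study". Section 9.1.1.1 gives the procedure: "Subjects will be monitored at each study visit for adverse events", by an open-ended question, and "A specific enquiry will be made at the time of each check-in". It does not define a check-in. The flow chart (section 4) has one safety row, "Complications", marked at 4 and 8 weeks and blank at 6 and 12 months. After the end-of-study visit at week 8, section 8.1.1 says "There are no other scheduled visits for this study".

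**After week 8.** In the leva arm, "patients will be recommended to continue weekly pelvic floor muscle exercises using the leva device" (section 8.1), and the reminder sub-group gets text prompts for a further 10 months. Section 11.5 lets women keep the device. Section 8.1 introduces the late contacts with "The 6 and 12 months follow-up by phone and email or mail will include" and then lists the questionnaires. The arm descriptions and the flow chart add a report of any further treatment for stress incontinence. None of these places lists an adverse-event item.

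**Analysis.** Section 7.2 names AEs and SAEs as the safety endpoint, and section 10.1.2 defines a safety population. Section 10.2 plans a listing by subject, and section 10.1 leaves detailed methods to the Clinical Study Report. The SAP contains no AE, SAE or complication outcome. Its nearest items are technical-issue calls in the leva arm (3.2.2) and the McGill Pain Questionnaire (3.4).

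**The concern.** There are two separate gaps.

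The first is in collection. The planned enquiry stops while use of the device is still being recommended. Section 8.2 says of leva Plus that the "device has not been submitted to FDA for approval yet", and describes a patient-contacting material different from that of the predicate device. Long-term maintenance therapy is also one of the primary objectives (section 7.1), so the later phase is meant to answer a study question. Anyone reporting on maintenance use would have efficacy data to month 12 but no systematic harms data beyond week 8.

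The second is in analysis. A stated endpoint has no planned summary by randomised arm. A listing shows events one woman at a time. It gives no proportion, denominator or measure of precision, and it leaves the choice of what to tabulate until the data have been seen.

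**Working it through.** The documents give no safety figure to reproduce, so this is mainly a comparison of passages, with two short calculations.

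**1. Schedule against recommended use (Protocol)**

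| Period | Recommended leva use (8.1) | Planned AE enquiry |
|---|---|---|
| Baseline to week 8 | Twice daily, 7 days a week | Weeks 4 and 8 (flow chart; 9.1.1.1) |
| Week 8 to month 12 | Weekly; prompts for about 10 months in the reminder sub-arm only | None listed (flow chart; 8.1 list of late contacts) |

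Section 9.1.1.2 adds a route that does not depend on visits: SAEs are reported once the site learns of them. Non-serious AEs have no such route.

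**2. Length of the uncovered period.** Section 8.1 counts the late contacts from baseline in the arm descriptions, but from the end of the study in its opening bullets.
- From baseline: 52 − 8 = 44 weeks.
- From the end of the 8 weeks: 60 − 8 = 52 weeks.

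**3. The same gap in device sessions.** This assumes that weekly means one session a week.
- Covered: 14 sessions a week × 8 weeks = 112.
- Uncovered: 44 or 52 sessions.
- Covered share: 112/(112 + 44) = 112/156 = 72%, or 112/(112 + 52) = 112/164 = 68%.

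So about 70% of the recommended sessions fall inside the covered 8 weeks.

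**4. Analysis.** Protocol 7.2 (endpoint) and 10.1.2 (population) call for a safety evaluation. Protocol 10.2 supplies only a listing, and SAP sections 1 to 4 supply nothing. SAP 4.2 allows further analyses at discretion, which does not pre-specify one. The denominators also differ. Protocol 10.1.2 requires at least one training session, while SAP 3.5 uses all randomised women. How the first rule applies to Kegel women is not stated, and section 8.4.2 says that their compliance is not monitored.

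**5. Why an interval should accompany the counts.** SAP section 2 gives 30 women per arm. For an illustrative 0 events in 30, the upper exact two-sided 95% limit is 1 − 0.025^(1/30) = 0.116, or 11.6%. The one-sided 95% limit is 1 − 0.05^(1/30) = 0.095, or 9.5%. These limits follow from n = 30 and do not measure the gap. They show what a bare listing would leave unsaid.

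**The case against.** The strongest reply is that the protocol treats the study as 8 weeks. The synopsis and section 8.1.1 call week 8 the end-of-study visit. Section 8.1 sets participation at 8 weeks and places the surveys after it, and section 8.3.1 speaks of an 8-week study. On that reading, section 10.2 agrees with the flow chart. This stands: a reader might infer a flat contradiction, but the text is ambiguous. What remains is recommended device use with no planned AE enquiry, alongside a primary objective on long-term maintenance.

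Other parts of the reply also hold.
- SAEs are reported on awareness, the undefined check-in might include calls, and section 8.1 allows for unscheduled visits. Collection is therefore not strictly confined to weeks 4 and 8; only the scheduled enquiry is.
- The late contacts do more than repeat incontinence scales. They ask about further treatment and include the McGill Pain Questionnaire, so pain, one plausible device harm, is asked about. That is still not AE collection.
- A reader might take 8/52 = 15% as the share of device use under observation. That ratio counts calendar weeks. By sessions the share is about 70%, on the assumption above.
- A reader might infer that all leva women are told to use an unapproved device until month 12. Use is recommended, other treatments are allowed, and only one sub-arm is prompted. The regulatory statement holds at the protocol's date, when a submission was planned. The same section classes the device as non-significant risk, and its later status is not in the documents.
- A reader might infer that the trial could support no safety statement at all. With 30 women per arm, listings can be counted by arm afterwards. The fault is that no such summary is planned.

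**Conclusion.** The concern holds as two gaps of unequal practical weight.

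- **Collection (protocol).** No AE enquiry is scheduled for the 44 or 52 weeks after week 8, although weekly leva use is recommended then. Non-serious AEs in that phase would be missed, and SAEs would depend on a site hearing of them. Because the meaning of the study period is ambiguous, sections 4, 8.1, 8.1.1, 9.1.1.1 and 10.2 must be reconciled. This does not affect the pilot data: SAP section 2 reports that the trial ended early with 60 women followed for 8 weeks.
- **Analysis (SAP).** A protocol endpoint has no by-arm summary. This applies in full to the 8-week pilot data.

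Neither gap alters the sample size or any efficacy analysis. The conclusion assumes that the single safety row of the flow chart is where AEs are recorded, and that the listed content of the late contacts is complete. Both should be corrected; the SAP table is the part with immediate effect.

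**What to change.** 1. **Protocol.** State the AE collection period in section 10.2. Add the open-ended question of section 9.1.1.1 to the 6- and 12-month contacts already scheduled, mark the safety row of the flow chart at those times, and define check-in. The cost is one question per contact and some data entry.

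2. **SAP.** Add one table by randomised arm, through week 8, with the number and percent of women having any AE, any SAE, a device-related AE where relatedness was recorded, and withdrawal because of an AE, each with an exact 95% interval. The qualifier on relatedness is needed because the protocol describes no relatedness assessment for non-serious events. State whether the denominator is the safety population of Protocol 10.1.2 or all women randomised (SAP 3.5), and how the requirement of at least one training session applies to the Kegel arm. The cost is one table from data that the protocol already requires.
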